7.2.2 Rationale for trial Population

Tirbanibulin is approved for the field treatment of non-hyperkeratotic, non-hypertrophic AK (Olsen grade 1) of the face or scalp in adults. The trial population will consist of male and female adult patients with 4-8 non-hyperkeratotic non-hypertrophic AK lesions of the face or scalp in a 25 cm² area who have not been previously treated in the same area in the last 6 months. A minimum of 30% of patients previously treated in other small areas (up to 25cm²) in the last >1 to <6 months to avoid patient recall bias from previous treatments will be enrolled.

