11.4 Analysis of Secondary Endpoints

Patient-reported outcomes

- The mean or median change from baseline in total Skindex-16 and its components at Day 57 will be estimated with 95% CI.
- The mean or median of the Likert Scale for organoleptic properties of tirbanibulin at Day 8 will be estimated with 95% CI.
- The mean or median for Convenience, Efficacy, Side Effects and Total satisfaction of TSQM 1.4 at Day 57 will be estimated with 95% CI.
- Treatment preference assessed through question 1 (Q1) to question 9 (Q9) of the EPQ at Day 57 will be summarized with frequency distribution and 95% CI for proportions.

Efficacy

- The percentage of patients with complete (100%) clearance of all lesions within the application area at Day 57 will be estimated with the 95% CI for proportions.
- The percentage of patients with partial clearance, defined as a reduction of at least 75% in the number of lesions within the application area, at Day 57 will be estimated with the 95% CI for proportions.
- The mean or median number of old and new AK lesions at Day 57 will be estimated with corresponding 95% CI.

- Olsen characterization at baseline (Day 0; pre-dose) and Day 57 will be summarized with frequency distribution and 95% CI for proportions.
- RCM and OCT of subclinical lesions (at only one selected site: Hospital Clinic de Barcelona) at baseline (Day 0; pre-dose), Day 8, Day 15, Day 29, and Day 57 will be summarized.

Physician reported outcomes

- Physician outcomes assessed at Day 57 through question 1 (Q1) to question 10 (Q10) of EPQ will be summarized with frequency distribution and 95% CI for proportions.

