11.4.1 Analysis of Safety and Tolerability Endpoints

The analyses of safety and tolerability outcomes will be performed on the Safety Population. Safety outcomes include adverse events, blood pressure and heart rate (vital signs).

LSRs

LSRs assessment results obtained through Day 57 will be summarized by visit reporting for each of the six signs (erythema, flaking/scaling, crusting, swelling, vesiculation/pustulation, and erosion/ulceration at the application-site) the number and percentage of patients corresponding to each of the score ranging from 0=absent to 3=severe. In addition, a composite score will be calculated as the sum of the scores for all six signs (range 0 to 18, with higher scores indicating more severe reactions) at each visit for each patient and summarized with standard summary statistics for continuous variables.

Application-site reactions such as application-site pruritus or application-site pain (including pain, tenderness, stinging, and burning sensation) not classified as LSRs will be reported as adverse events (AE)..

Adverse Events

The incidence of AEs, SAEs and AESI recorded throughout the study will be summarized by MedDRA SOC and PT. A summary of AEs by SOC, PT and severity will be also provided. All related AEs, SAEs, AEs with an outcome of death, AEs leading to treatment discontinuation will be summarized by MedDRA SOC and PT. Deaths will be listed together with all relevant information.

The frequency of comorbidities will be analyzed descriptively.

Vital Signs

Vital signs (blood pressure and heart rate) will be summarized at each time point and as change from screening value with descriptive statistics.

Medication Adherence

Medication adherence assessed with patient-kept diary will be summarized with frequency distribution from Day 0 to Day 4

11.4.2

Analysis of Pharmacokinetic Parameters

Not applicable

11.4.3

Pharmacokinetic/Pharmacodynamic Analysis

Not applicable

11.5

Handling of Missing Data

In case of missing values, no imputation will be done. Further details on the handling of missing data will be provided in the SAP.

11.6

Multiplicity Strategy

No statistical test will be conducted, so there is no need to consider multiplicity issue.

11.7

Interim Analysis

An intermediate descriptive analysis is planned when 50% of patients have completed the study. Further details will be provided in the SAP.

12 Data Handling, Processing, and Record Keeping

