6.3.2.2. Likert Scale for organoleptic properties of Tirbanibulin

Definition

Likert scale is an instrument used to measure the individual's degree of agreement and disagreement with a variety of statements about some attitude, options, or their

	
Statistical Analysis Plan

	
Sponsor: ALMIRALL, S.A.

	
Protocol number: M-14789-42

feelings. In this study, the product's organoleptic properties are evaluated with Likert scale. The questionnaire is built with questions related to the product's characteristics namely appearance, color, convenience, texture, smell, and the feelings experienced during drug application. The Likert scale offers 7 possible answers, from "totally agree" to "totally in disagreement".

In this secondary objective the main purpose is the description of organoleptic properties (i.e appearance, color, convenience, texture, smell, and the feelings experienced during drug application) of Tirbanibulin through the Likert Scale at Day 8.

Analysis methodology

The number and percentages of patients who completed the questionnaire at Day 8 (i.e. Visit 3) will be summarized.

Scores of each question obtained by patients will be summarized with descriptive statistics and 95% CI (calculated for the multinomial proportion) of each question' response will be provided. In case the lower limit of CI is negative due to small frequency of the category, 0 will be imputed as lower limit.

Data handling rules

No missing imputation will be performed.

Sensitivity of secondary analysis

Not applicable.

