6.3.2.4. EPQ questionnaires

Definition

EPQ was developed to accommodate an adequate validity as a real-world evidence tool to solicit patient's treatment preference and physician treatment outcomes. EPQ consists of 10 specific items to identify both patient and physical treatment preference. EPQ comprises of 2 versions, namely clinician and patient version. Clinician's version comprises 10 questions and patient's version includes 9 questions. The questions used in both the versions are similar, but they have been reworded to address both clinician and patient. Clinician version of the EPQ will be administered

	
Statistical Analysis Plan
 
Sponsor: ALMIRALL, S.A.
 
Protocol number: M-14789-42

---	---

to the clinician through physician reported outcome booklet. Patient version of the EPQ will be administered to the patients through patient reported outcome booklet.

Patient treatment preference at Day 57 will be assessed through question 1 (Q1) to question 9 (Q9) of the EPQ (whose outcome are reported in EPQ (PATIENT VERSION) eCRF pages) as well as physician treatment preference at Day 57 through question 1 (Q1) to question 10 (Q10) of EPQ (whose outcome are reported in EPQ (CLINICIAN VERSION) eCRF pages).

Analysis methodology

All the analysis on EPQ questionnaires will be provided by country, by AK previous naïve status (i.e., naïve patients are patients never previously treated for AK lesions; not naïve patients are patients already treated for AK lesions) and overall.

The number and percentages of patients and physicians who completed the respective questionnaire at Day 57 (i.e., Visit 4) will be summarized. The proportion of patients for each response provided by patients and clinicians will be computed with the corresponding 95% CI for the multinomial proportion. In case the lower limit of CI is negative due to small frequency of the category, 0 will be imputed as lower limit.

Data handling rules

No missing imputation will be performed.

Sensitivity of secondary analysis

Not applicable.

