6.3.2.6. Olsen characterization of AK lesions

Definition

The lesions in the identified treatment area will be classified based on Olsen characterization. It consists in the following grades:

- *Olsen Grade I*: Early AK appear as single or few, differently sized, from 0.1-0.3-5.0 cm, in size, rough, blurred, less visible than palpable (palpable on the roughness of the surface), red, rough spots or very flat, non-edged plaques which reach into the reddish colour and are easier to feel than to see;
- *Olsen grade II*: describes advanced AK as clearly visible and palpable, flat, and irregularly raised, with sharp or blurred boundaries, red, rough keratinized surface. If the surface is more strongly keratinized, the AK can also be white, yellow, or light brown. After scratching effects (frequently), a black or blue-black shade may appear (older bleeding);
- *Olsen grade III*: denotes "late" AK that have existed for a longer period of time and are firmly anchored on the lower surface, with an irregular, humpy surface, also wart-like and of different colours (white, brown, black). When the horn deposits are removed, an erosive subsurface is formed.

Olsen characterization (whose outcome will be reported in "AK LESION COUNT AND OLSEN GRADING" eCRF pages) will be evaluated for each patient at Baseline Visit and at Final Visit.

Therefore, in this analysis, the following groups will be considered:

- Olsen I: patients with all lesions graded as Olsen I;
- Olsen II: patients with all lesions graded as Olsen II;
- Olsen III: patients with all lesions graded as Olsen III;
- Olsen I/II: patients with some lesions graded as Olsen I and some lesions graded as Olsen II;

	
Statistical Analysis Plan

	Sponsor: ALMIRALL, S.A.
	Protocol number: M-14789-42

- Olsen I/III: patients with some lesions graded as Olsen I and some lesions graded as Olsen III;
- Olsen II/III: patients with some lesions graded as Olsen II and some lesions graded as Olsen III;
- Olsen I/II/III: patients with some lesions graded as Olsen I, some lesions graded as Olsen II and some lesions graded as Olsen III;

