- Complete clearance (Only for Final Visit): patients who performed Olsen Grade evaluation (i.e., patient who answered “Was OLSEN Grading performed? = Yes” in AK LESION COUNT AND OLSEN GRADING eCRF Page) and reported no lesions or patients who did not perform Olsen Grade evaluation because he/she specified no lesions observed (specified in AK LESION COUNT AND OLSEN GRADING eCRF Page);
- Missing: patients with AK lesions who did not perform Olsen Grade evaluation for at least one of them.

Analysis methodology

The number and percentages of patients who performed the AK lesions Olsen Grading at each timepoint (i.e., Baseline Visit and Final Visit) will be reported.

The proportions of patients with lesions classified as described above at Baseline and at Final Visit will be provided with the corresponding 95% CI calculated for the multinomial proportion. In case the lower limit of CI will be negative due to small frequency of the category, 0 will be imputed as lower limit.

Furthermore, a shift table Baseline vs Final Visit with frequency distribution will be produced.

Data handling rules

No missing imputation will be performed.

Sensitivity of secondary analysis

Not applicable.

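### The multinomial 95% CIs for the Likert, EPQ and Olsen tables name neither the method nor the type of coverage, their cut-at-zero rule points to limits that handle rare categories poorly, and the clinician EPQ interval makes no allowance for shared raters

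*SAP*

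**What the plan says.** Three SAP sections use the same interval: 6.3.2.2 (Likert scale), 6.3.2.4 (EPQ, patient and clinician versions) and 6.3.2.6 (Olsen grading). The EPQ section says: "The proportion of patients for each response provided by patients and clinicians will be computed with the corresponding 95% CI for the multinomial proportion". The Likert section adds: "In case the lower limit of CI is negative due to small frequency of the category, 0 will be imputed as lower limit". The EPQ section repeats that rule, and the Olsen section has it almost word for word: "In case the lower limit of CI will be negative due to small frequency of the category, 0 will be imputed as lower limit".

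The protocol is no more specific. Section 11.4 says that patient preference from Q1 to Q9 "of the EPQ at Day 57 will be summarized with frequency distribution and 95% CI for proportions". SAP 4.1 fixes the level (two-sided 0.05) but not the method. Elsewhere the SAP does name its methods: the exact binomial for clearance (6.3.2.5) and Student's t for means (6.3.1).

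On the raters, SAP 3.4 has the investigators complete the clinician EPQ at Day 57, SAP 3.1 plans at least 10 patients per site, and SAP 4.6 pools all centres. No section adjusts an interval for site or rater.

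**The concern.** Two programmers could follow these sections faithfully and produce different tables, and a reader could not tell which coverage is claimed. The cut-at-zero rule adds to this, because it is needed only for methods whose lower limit can fall below 0. The usual multinomial methods of that kind serve rare categories badly, either by excluding true values too often or by being far too wide.

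Rare or empty categories should be expected. For the organoleptic items, "The Likert scale offers 7 possible answers". The Olsen table has four groups that involve grade III, among them "Olsen III: patients with all lesions graded as Olsen III", while Protocol 7.2.2 describes the product as "approved for the field treatment of non-hyperkeratotic, non-hypertrophic AK (Olsen grade 1) of the face or scalp in adults" and recruits that lesion type.

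The clinician EPQ raises a second matter. Answers from one clinician about several patients are plausibly alike. SAP 3.1 says that sites were chosen to reflect variation in real-world care, so readers will generalise beyond these raters. An interval that counts each form as independent may then show more certainty than the data hold. With no tests planned, the interval is the only statement of precision for these proportions.

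**Working it through.** The plan gives no precision figure for these intervals. Its only such figure concerns TSQM-9 means, and the checks below do not use it.

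**Inputs**
- n = 420 overall (SAP 3.1) and n = 70 for Italy (Protocol 8.1). The EPQ is tabulated by country, so n = 70 applies to Italy's EPQ table. Losses before Day 57 would lower both numbers.
- 7 categories, as for the Likert items. The number of EPQ answer options is not stated.
- 42 sites (Protocol) or 37 (SAP 3.1; SAP 4.6 gives about 40).
- True category frequencies and the ICC are assumptions.

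**1. Category with no responses: lower limit 0, upper limit as shown**

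| Method | Formula at count 0 | n=70 | n=420 |
|---|---|---|---|
| Wald | 0 + 1.96·√(0·1/n) | 0 | 0 |
| Wilson | 1.96²/(n + 1.96²) = 3.84/73.84; 3.84/423.84 | 5.2% | 0.9% |
| Exact | 1 − 0.025^(1/n) | 5.1% | 0.9% |
| Goodman, 7 categories | 2.690²/(n + 2.690²) = 7.24/77.24; 7.24/427.24 | 9.4% | 1.7% |
| Fitzpatrick-Scott | 1.1285/√n | 13.5% | 5.5% |
| Sison-Glaz | computed on assumed tables | 12.1 to 12.9% | 4.8 to 5.2% |
| Agresti-Coull | Wald form at adjusted count and n | 6.2% | 1.1% |

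Wilson, exact and Goodman lower limits are never negative. Wald limits are negative at small non-zero counts. At 1 of 420, for example, 0.24% ± 0.47% gives −0.23% to 0.70%. Sison-Glaz and Fitzpatrick-Scott limits also go below 0, and so do Agresti-Coull limits at counts 0 and 1.

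**2. Per-category coverage of a true 1% category (exact binomial)**
- Wald, n=70: a count of 0 gives [0, 0] and misses. Its probability is 0.99^70 = 0.495. Counts of 5 or more also miss (0.001). Coverage is 1 − 0.495 − 0.001 = 50%.
- Wald, n=420: counts of 0 (0.015), 1 (0.062) and 11 or more (0.004) miss. Coverage is 1 − 0.081 = 92%.
- Wilson: 97% (n=70) and 96% (n=420).
- Agresti-Coull: 99.5% and 97.3%.
- Sison-Glaz and Fitzpatrick-Scott (simulated): 100%, with mean widths of 13 to 14.5 points (n=70) and 6 to 6.5 points (n=420), against 6.6 and 2.0 for Wilson.

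**3. Per category or joint**

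This was simulated for three assumed 7-category tables with two or more rare categories. Per-category Wilson limits hold for all seven at once in 71 to 75% of samples. Goodman limits do so in 93 to 95% at n=420 and 84 to 90% at n=70. The two readings of 95% are therefore different claims.

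**4. Clinician EPQ, 50% response**

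Unadjusted half-width: 100 × 1.96 × √(0.25/420) = 4.8 points. With m = 420/42 = 10 forms per site, the design effect is 1 + (10 − 1) × ICC, and the half-width is multiplied by its square root.

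| Assumed ICC | Design effect | Half-width, 42 sites | Half-width, 37 sites (m = 11.35) |
|---|---|---|---|
| 0.05 | 1.45 | 5.8 | 5.9 |
| 0.10 | 1.90 | 6.6 | 6.8 |
| 0.20 | 2.80 | 8.0 | 8.4 |

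With 42 sites, an unadjusted interval would then cover about 90%, 84% and 76%, from 2Φ(1.96/√design effect) − 1.

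**The case against.** A reader might infer that the cut-at-zero rule excludes every sound method, so that a poor one is certainly planned. The documents do not support that. The sentence is conditional. Under Wilson or Goodman limits it would simply never apply, so it makes them unlikely but does not rule them out. Agresti-Coull limits do go negative and still cover rare categories well. They are a per-category binomial interval and an unusual reading of a multinomial CI, but they fit the text.

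A reader might also infer that the clinician EPQ intervals are too narrow by a known amount, or that the primary TSQM-9 precision fails for the same reason. Neither follows. The documents give no ICC and no number of clinicians per site. Sites were selected by region and size, not sampled at random, so a site-clustered interval is itself a modelling choice. For TSQM-9 the stated ±1.6 to ±2.1 leaves some slack over the simple calculation (1.96 × 15/√420 = 1.43; 1.96 × 20/√420 = 1.91).

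Three further points stand:
- Counts and percentages appear beside each interval, so a reader would see 0 of 420.
- The 50% coverage figure needs both n=70 and a true frequency of 1%.
- The SAP contents list an appendix that is not in the text available for review. If it names the method, the first part reduces to a missing cross-reference.

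None of this supplies the method or the type of coverage in the three sections, or an allowance for shared raters.

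**Conclusion.** The point holds as a minor one. In the available text, the interval method and the type of coverage are unspecified in three sections. The cut-at-zero rule makes Wald-type or fixed-width limits likely, not certain. If one of these is used, an unused category at n=420 would read [0, 0] or about 0 to 5%, where Wilson gives 0 to 0.9%. At n=70 it would read [0, 0] or about 0 to 13%, where Wilson gives 0 to 5.2%.

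That the clinician EPQ interval ignores shared raters is a fact of the plan. How much this matters depends wholly on the assumed ICC, and on whether the result is meant to speak beyond the participating clinicians.

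These are descriptive secondary tables. Protocol 11.6 says "No statistical test will be conducted, so there is no need to consider multiplicity issue", and no decision rule or primary result changes.

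**What to change.** **Interval method.** In SAP 6.3.2.2, 6.3.2.4 and 6.3.2.6, delete the cut-at-zero sentence. Name Wilson 95% limits per category, label them as per-category coverage, and give them for empty categories too. This suits a plan without tests or multiplicity adjustment. If joint coverage is intended, name Goodman limits and the actual number of categories in each table. The Olsen table has seven grade groups and a missing group, and at Day 57 also a complete-clearance group. It must be stated whether the missing group counts.

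**Clinician EPQ.** Keep the planned tables. Beside the overall proportions add a supportive site-clustered 95% CI, for example Wilson limits on the effective sample size with t on sites − 1 degrees of freedom. Report the ICC and the number of clinicians. Restrict it to categories that are not rare, with the cut-off set in advance; about 20 responses is a workable choice, but it is a judgement. Do not add it by country, since Italy has only 7 sites.

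**Disclosure.** Record both as changes made after the interim analysis described in SAP 6.6.

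**Cost.** The change needs a few sentences and little programming, because the site identifier is already used to derive country (SAP 6.5). Each clinician EPQ question gains a second interval. The clustered limits are slightly wider even if the ICC is 0. Per-category limits give no joint coverage and must be labelled so. Goodman limits are wider and still fall somewhat short of 95% jointly at n=70.

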6.3.2.5. AK lesions characteristics

Definition

For each patient the following assessments (reported in AK LESION COUNT and in AK LESION COUNT AND OLSEN GRADING eCRF pages) will be provided:

- Presence of AK lesions (counted only if they are inside the treatment area) at Screening and Baseline and count of new and old AK lesions ad Day 57
- Reduction of number of lesions at Day 57 will be calculated considering only old lesions as:

	
Statistical Analysis Plan
 
Sponsor: ALMIRALL, S.A.
 
Protocol number: M-14789-42

---	---

$$\frac{N. \text{ lesions at Baseline} - N. \text{ old lesions at Day 57}}{N. \text{ lesions at Baseline}} * 100\%$$

N. old lesions at day 57 is reported in AK LESION COUNT AND OLSEN GRADING eCRF page.

- Reduction of number of lesions at Day 57 will be calculated considering considering both old and new lesions, as:

$$\frac{N. \text{ lesions at Baseline} - N. \text{ lesions at Day 57}}{N. \text{ lesions at Baseline}} * 100\%$$

Where, N. lesions at day 57 = N. new lesions + N. old lesions reported in AK LESION COUNT AND OLSEN GRADING eCRF page.

- Occurrence of complete clearance of all AK lesions within the application area, is defined as a reduction from baseline in the number of lesions = 100% at day 57
- Occurrence of partial clearance is defined as a reduction $\geq 75\%$ in the number of lesions within the application area at Day 57.

Analysis methodology

All the analysis reported in this section will be provided by country, AK lesion localization and overall.

The number and percentages of patients who performed the AK lesions count at each timepoint (i.e., Screening Visit, Baseline Visit and Final Visit) will be reported.

The number of the AK lesions at Screening, Baseline and Final Visit (new, old and total AK lesions) will be provided.

The change from Baseline Visit of the AK lesions count will be described at Final Visit reporting also the corresponding 95% CI estimated by Student's t distribution, regardless response's distribution.

The number and percentages of patients with a complete clearance will be provided with the corresponding 95% CI calculated with the Binomial exact method.

	
Statistical Analysis Plan
 
Sponsor: ALMIRALL, S.A.
 
Protocol number: M-14789-42

---	---

Similarly, the same analysis will be performed for patients with partial clearance. In order to verify the association between Olsen Grade (defined in Section 5.3.2.6) and clearance, a cross-table between their categories will be produced.

Data handling rules

No missing imputation will be performed.

Sensitivity of secondary analysis

Not applicable.

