3.3.3. Prior and Concomitant Therapy

Since this is a single arm study, no control treatment or other treatments beyond IMP Tirbanibulin will be included in this study.

It will be mandatory to report on the appropriate electronic Case Report Form (eCRF) page information relative to concomitant prescription medications, over-the-counter medications, and supplements.

As regards to pre-trial medications, each patient's complete AK treatment history of face and scalp will be recorded on the eCRF as well as any treatment (prescription and non-prescription including vitamins and dietary supplements) and procedure taken during the 28 days before Day 0. Patients must not have received any IMP within the preceding 30 days from the first trial drug administration or any medication that could not be eliminated from the body (5 elimination half-lives of the IMP).

Regardless to concomitant medications, during the follow-up period (period between Visit 3 and Visit 4, i.e. from Day 8 to Day 57), only medications/therapies for the treatment of Adverse Events (AEs) in the treatment area and those that may affect the assessment of AK lesion recurrence in the treatment area will be entered in eCRF page as well as any topical products for treatment of local skin reactions/local tolerability signs in the treatment area allowed by the Investigator from Day 8 up to Day 57.

	
Statistical Analysis Plan
 
Sponsor: ALMIRALL, S.A.
 
Protocol number: M-14789-42

---	---

Use of any treatment for AK lesions other than study drug on the treatment area will be prohibited during the study. Subjects will be reminded that AK lesions located outside the treatment area may be treated by lesion-directed treatment only, e.g., cryotherapy or biopsy. A detailed list of prohibited medications is provided in section 9.6.3 Prohibited Medications/Therapy of the study protocol. There are no restrictions during the study on smoking/tobacco use, diet, alcohol/caffeine, water or other beverages, or physical activity. Once the last Tirbanibulin dose will be applied and related trial measurements will be completed, patients should continue to take their usual medications, also allowed during the trial, and may resume other medications interrupted prior to trial enrolment as deemed appropriate by the Investigator; while it is not planned to treat patients with Tirbanibulin any further than scheduled in this trial.

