4.3. Coding of Therapies and Medical Terms

Medications/therapies reported in PRIOR AND CONCOMITANT MEDICATIONS/THERAPIES eCRF pages will be coded using version B3_Q1_2023 of the World Health Organization (WHO) dictionary. Medical terms reported in the MEDICAL HISTORY, SURGICAL AND MEDICAL PROCEDURES or ADVERSE EVENTS eCRF pages are coded using version ENG 26.0 of the Medical Dictionary for Regulatory Activities (MedDRA).

	
Statistical Analysis Plan

	Sponsor: ALMIRALL, S.A.
	Protocol number: M-14789-42

Versions of the dictionaries can be upgraded during the study according to Sponsor's request.

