5. ANALYSIS POPULATIONS

Starting from Screened patients (i.e., all patients who signed the informed consent form), the following analysis populations will be defined for statistical analysis:

- **Enrolled population:** all patients who signed the informed consent form and completed the screening disposition.
- **Full analysis set (FAS) population:** all patients who signed the informed consent form and applied at least one dose of Tirbanibulin.
- **Evaluable patient population:** FAS patients who completed the 57 days of observation and have the TSQM-9 assessment.
- **Safety patient population:** Full analysis set patients.
- **LC-OCT Population:** FAS patients who performed at least one valid LC-OCT assessment (i.e., FAS patients enrolled at site 101).

	Statistical Analysis Plan Sponsor: ALMIRALL, S.A. Protocol number: M-14789-42
---	--

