6.4.2. Concomitant medications

Concomitant medications are defined as therapies ending or ongoing after the first Tirbanibulin application.

Since no imputation will be performed in case of partial/missing medication's start or end date, the presence of at least one of the following conditions will be used to identify concomitant medication:

- If medication status is ongoing;
- If medication end date is missing and medication status is not ongoing or missing;
- If medication end date is complete, medication status is not ongoing or missing and medication end date \geq Tirbanibulin start date;

	Statistical Analysis Plan Sponsor: ALMIRALL, S.A. Protocol number: M-14789-42
---	--

- If day and month of medication end date are missing, medication status is not ongoing or missing and medication end date year \geq Tirbanibulin start date year;
- If only day of medication end date is missing, medication status is not ongoing or missing and medication end date year $>$ Tirbanibulin start date year;
- If only day of medication end date is missing, medication status is not ongoing or missing, medication end date year = Tirbanibulin start date year and medication end date month \geq Tirbanibulin start date month.

Concomitant medications/therapies and surgical/medical procedures will be described by ATC code (2nd level class) and Preferred Term, presenting the number and percentage of patients taking at least one concomitant medication/procedures.

Moreover, surgical and medical procedures administrated to each patient will be described by System Organ Class and Preferred Term, presenting the number and percentage of patients undergoing at least one surgical or medical procedure.

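### Clearance is scored on the Day 57 lesion count alone, so a patient who completes after recorded, prohibited lesion-directed therapy inside the treatment area can be counted as cleared by tirbanibulin

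*SAP*

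**What the plan says.** **Scoring.** SAP 6.3.2.5 computes a percent reduction from the baseline and Day 57 counts. Complete clearance "is defined as a reduction from baseline in the number of lesions = 100% at day 57". For the lower threshold, "Occurrence of partial clearance is defined as a reduction" of at least 75% within the application area. In SAP 6.3.2.6 the Complete clearance category at the final visit rests on no lesions being reported, and it includes "patients who did not perform Olsen Grade evaluation because he/she specified no lesions observed". None of these definitions mentions other therapy.

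**Prohibition and recording.** SAP 3.3.3 states: "Use of any treatment for AK lesions other than study drug on the treatment area will be prohibited during the study". For follow-up, the same section says that AE treatments in the area and "those that may affect the assessment of AK lesion recurrence in the treatment area will be entered in eCRF page". There is also a procedures page: "Medical terms reported in the MEDICAL HISTORY, SURGICAL AND MEDICAL PROCEDURES or ADVERSE EVENTS eCRF pages are coded" (SAP 4.3).

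**Use of these records.** SAP 6.4.2 tabulates them: "surgical and medical procedures administrated to each patient will be described by System Organ Class and Preferred Term". SAP 6.1 summarises and lists protocol deviations.

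**Analysis set.** Clearance is analysed on the Evaluable population, "FAS patients who completed the 57 days of observation and have the TSQM-9 assessment" (SAP 5). SAP 6.3.2 takes all collected data into account. Table 5.1-1 has three exclusion codes: no study drug applied, discontinuation before Visit 4, and no valid LC-OCT. SAP 6.3.2.5 and 6.3.2.6 both mark sensitivity analysis as not applicable.

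**Withdrawal.** Protocol 9.6.3 (v1.0) withdraws patients who begin a systemic or a topical AK treatment. It mentions lesion-directed treatment separately, as something allowed only outside the area. Under Protocol 8.5 the investigator may withdraw a patient for marked non-compliance or by physician decision, but need not.

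**The concern.** The clearance rate will be read as what tirbanibulin achieved. If a residual lesion in the field is removed by cryotherapy or curettage before Day 57, the count falls for a reason unrelated to the drug, and the stated rule credits the drug with it. The misclassification goes one way only: removing a lesion cannot make a patient look less cleared. The trial has a single cohort, so there is no control arm in which the error could cancel.

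The setting makes the event conceivable. Patients are managed by dermatologists, and lesion-directed treatment is permitted just outside a field of at most 25 cm². Because the plan has no rule for such patients, any decision to treat them differently would be taken after the data had been seen.

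**Working it through.** The plan gives no precision or sensitivity figure for clearance, so there is none to reproduce. The check traces a patient through the rules and then bounds the effect.

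**1. Does a treated completer stay in and count as cleared?**
- Prohibited: yes (SAP 3.3.3; Protocol 9.6.3).
- Mandatory withdrawal: not clearly. Protocol 9.6.3 names systemic and topical therapy. The protocol elsewhere keeps procedures apart from topical products: exclusion criterion 9 lists liquid nitrogen, excision and curettage as procedures, and section 5.1.1 separates cryosurgery from topical agents.
- Discretionary withdrawal: possible under 8.5.
- Removed from the Evaluable population: only if the patient discontinues or lacks the TSQM-9. No code covers prohibited therapy.
- Scored: on the Day 57 count as observed.

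A patient who is not withdrawn therefore completes and is scored on a count that the other therapy has lowered. SAP 6.3.2.5 gives two reductions (old lesions only; old plus new) without saying which defines clearance. A removed baseline lesion lowers the count under both.

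**2. When does one removed lesion change the class?** Inclusion requires b = 4 to 8 baseline lesions.
- Complete clearance: one lesion left, reduced to none.
- Partial clearance: (b − residual)/b ≥ 0.75, so residual ≤ b/4. The largest passing residual is 1 for b = 4 to 7 and 2 for b = 8.

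| Baseline | Residual before → after | Reduction before → after |
|---|---|---|
| 4 | 2 → 1 | 50.0% → 75.0% |
| 5 | 2 → 1 | 60.0% → 80.0% |
| 6 | 2 → 1 | 66.7% → 83.3% |
| 7 | 2 → 1 | 71.4% → 85.7% |
| 8 | 3 → 2 | 62.5% → 75.0% |

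**3. Effect per patient.** 1/420 = 0.238 percentage point. If 10% were not evaluable (an assumption), N = 378 and 1/378 = 0.265 point.

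**4. Effect over assumed rates.** Rise = r × f, where r is the share of Evaluable patients with in-area therapy and f is the share of those whose class changes. The documents give neither, so r is assumed and f runs from 0 to 1.

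| Assumed r | Patients of 420 | Rise in clearance |
|---|---|---|
| 1% | about 4 | 0 to 1 point |
| 2% | about 8 | 0 to 2 points |
| 5% | 21 | 0 to 5 points |

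The lower end applies if every treated patient would have cleared anyway or still misses the threshold. The upper end applies if every one changes class.

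**5. Comparison with sampling error.** SAP 6.3.2.5 specifies the exact binomial interval. For illustration I use complete-clearance rates of 44% and 68% (Protocol 5.1.4) and 54% (Protocol 5.2, which gives a different figure for the second trial). Patients needed = half-width × 420/100.

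| Cleared/N | Exact 95% CI | Half-width | Patients to equal it |
|---|---|---|---|
| 185/420 | 39.2% to 48.9% | 4.85 points | 20.4 |
| 227/420 | 49.1% to 58.9% | 4.87 points | 20.5 |
| 286/420 | 63.4% to 72.5% | 4.56 points | 19.2 |

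**6. Worst-case recoding (f = 1).** An observed 54.0% becomes 53.1%, 52.1% or 49.0% when 4, 8 or 21 patients are rescored as not cleared. An observed 44.0% becomes 43.1%, 42.1% or 39.0%.

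**The case against.** The strongest reply is that the plan does have a rule: use all data as observed. In a low-interventional, descriptive study, an observed-count rate answers a legitimate question, and scoring treated patients as failures answers another. The scenario also needs several things together: a breach of a study-long prohibition, no withdrawal, and a residual count next to a threshold. Deviations are listed, the same dermatologist counts at baseline and Day 57, and all sites but one have no scheduled visit between Day 8 and Day 57, so there are few scheduled occasions for in-area treatment.

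Much of this stands. It limits the likely size, and it is a good reason to keep the observed-count rate in the report. It does not remove the point: a deviation listing discloses the breach but leaves the clearance rate unchanged, and that rate will be read as the drug's result.

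A reader might also infer more than the documents support:
- *Detected topical or systemic users are counted as cleared.* Under Protocol 9.6.3 (v1.0) they are withdrawn, and discontinuation before Visit 4 takes them out of the Evaluable population.
- *Undetected use is part of the defect.* It might occur, but no scoring rule could act on therapy that nobody recorded.
- *The primary TSQM-9 result is biased through these withdrawals.* The SAP follows protocol v3.0 (Spain) and v2.0 (Italy), which were not available. Neither the current withdrawal wording nor any satisfaction deficit in such patients can be established.

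**Conclusion.** The point holds for one group: Evaluable patients with recorded, prohibited lesion-directed AK therapy inside the treatment area before Day 57. For them the stated rule credits tirbanibulin with a lesion that something else removed. The bias can only be upward, at 0.24 point per misclassified patient with N = 420.

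The total effect is unknown. The 1% to 5% rates above are assumptions, every range starts at zero, and the documents do not support saying that the reported clearance rate is materially inflated. It is probably small, on a secondary and descriptive endpoint. The reading of the withdrawal rule rests on protocol v1.0. The SAP, which follows the later versions, repeats the prohibition and adds no scoring rule. This is a change to consider, not a serious flaw.

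**What to change.** **SAP 6.3.2.5.** Score any Evaluable patient with recorded non-study AK therapy in the treatment area between Day 0 and Day 57 as not cleared, for both complete and partial clearance. Confirm the indication and the anatomical site of each such record at data review, before database lock. Report the number of these patients, even if it is zero, and show the observed-count rate next to the main one.

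**SAP 6.3.2.6.** Leave the Olsen groups as they are, because a patient with no lesions has no grade and would fit no other row. Footnote the Complete clearance row with the number of such patients, or add a separate row for no lesions after other in-area therapy.

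**Cost.** One derivation rule, one count, one extra line per clearance table, and a check of therapy and procedure records. The eCRF already collects interfering in-area therapy, so no new data entry is planned. The downside is that a treated patient who would have cleared anyway is counted as not cleared, so the reported rate may be slightly lower. Showing both rates lets the reader see by how much.
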